Intervention: The definitive multi-faceted intervention will consist of the following components: (i) modified structured history of medication (mSHiM), (ii) Screening Tool of Older Persons' Prescriptions (STOPP) and Screening Tool to Alert to Right Treatment (START) screening for PIMs and PPOs using STOPP/START version 3, (iii) drug-drug interactions screening, using Stockley's Drug Interaction Checker (iv) face-to-face consultation with attending hospital physicians to discuss PIMs, PPOs, interactions and other issues, (v) pre-discharge medication review and adjustment, (vi) detailed medication adjustment discharge report to patients' general practitioners (GPs), (vii) follow-up contact with patients' GPs and community pharmacists at 1 week and 1 and 6 months post-discharge.

Patients in the control arm (standard pharmaceutical care) will receive a sham intervention i.e. modified Medication Adherence Rating Scale (MARS) questionnaire.

Outcome measures: Primary endpoints will include: (i) unscheduled readmission within 30 days post-discharge, (ii) unscheduled readmission within between 90 and 180 days post-discharge, and (iii) ED attendance within 30 days and between 90 and 180 days post-discharge. A primary composite endpoint of unscheduled readmission or ED attendance within 30 days and between 90 and 180 days post-discharge will also be ascertained. Secondary endpoints are: (i) quality of life measured by EQ5D-5L instrument (incorporating pain control) at 30 days and at between 90 and 180 days post-discharge, (ii) all-cause mortality at 30 days and at between 90 and 180 days post-discharge, (iii) first admission to residential care facility for long-term nursing care at 30 days and at between 90 and 180 days post-discharge. Treatment effects for each of the two active intervention arms (versus control) will be estimated and equivalence tests comparing the two active arms (for each outcome) will be undertaken to determine the effectiveness of the DI as delivered by a physician compared to a pharmacist.

An economic evaluation of the DI as delivered by a trained physician and by a trained pharmacist will also be undertaken, involving

- Quality Life Adjusted Year (QALY),
- cost per hospital readmission avoided, and
- cost per ED attendance avoided.

Time frame: 36 months from project start to final report submission.

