2.3 Research Question /Hypothesis

Hypothesis 1: A multi-faceted medication optimization definitive intervention (DI) based on explicit inappropriate prescribing criteria, potential prescribing omission criteria and drug-drug and drug-disease interaction surveillance applied following admission and pre-discharge from hospital in older people with multi-morbid illness and associate polypharmacy supplemented by structured follow-up with patients' GPs and community pharmacists as well with patients themselves results in significantly lower rates of unscheduled rehospitalization or emergency department attendance or both compared to standard current pharmaceutical care.

Hypothesis 2: The same multi-faceted medication optimization DI has an equal effect on rates of unscheduled rehospitalization or emergency department attendance or both when delivered by a trained pharmacist compared to a trained physician.

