4.3 Sampling and Randomization (if applicable)

To test the main study hypothesis i.e. that the definitive intervention (DI) yields significantly better outcomes than standard pharmaceutical care (control), patients will be randomized in a 1:1:1 ratio to one of 3 trial arms: (a) standard pharmaceutical care as it contemporaneously exists in that hospital, or (b) trained physician-delivered intervention or (c) clinical pharmacist-delivered intervention. The 3-way randomization to control, Physician-DI and Pharmacist DI is fundamental to addressing the important secondary question: does physician-delivered DI offer any advantage over pharmacist-delivered DI?

The sample size is based on a known 180-day risk of medication-related readmission of approximately 20%. At a bilateral 5% significance threshold and 80% power, for detection of an 8% absolute reduction in readmissions, with a 1:1:1 randomization, each group must contain 324 patients i.e. 972 patients in total. With the expectation of up to 30% patient attrition, we aim to randomize $972/(1-0.3) = 1389$ patients.

The randomization will be designed by the trial statistician, but the code to create the resulting randomization lists will be executed by an independent statistician. The resulting lists will be integrated into the electronic data capture system in a manner such that trial staff never have access to the lists. Allocation of enrolled patients into treatment arms will then be delivered using a web-based system, such that the allocation remains concealed until a patient is unambiguously consented and enrolled onto the trial and cannot be altered in the underlying database once it is revealed. While the intervention will be known to clinical staff, the trial statistician and outcome assessors will remain blinded until the results are finalized.

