4.0 Study Procedures and Schedule of Events

The schedule of trial procedures for patient participants in the intervention arm of the trial are shown in Tables 1a and 1b below. To mimic the intervention for blinding purposes of the participants, both control and intervention arm patients will receive a sham intervention in the form of a modified version of the Medication Adherence Rating Scale (MARS; Thompson et al.).

Table 1a: Schedule of events for intervention patients

Timepoints	0/1	2	3	4	5
Study Visit	Baseline (within 72 hours of admission)	Pre-discharge (within 48 hours pre-discharge)	1 Week Follow-up (within 10 days post-discharge)	1 Month Follow-up (within 30 days post-discharge)	6 Month Follow-up (between 90 and 180 days post-discharge)
	Day 1	Day variable	Day 10 (+/- 3 days post-discharge)	Day 30 (+/- 7 days post-discharge)	Between Day 90 and Day 180 post-discharge
Inclusion / Exclusion criteria	X				
Decision-Making Capacity Functional Assessment	X	X**		X**	X**
Informed consent/ proxy assent	X	X**		X**	X**
Patient Demographics	X				
Medical History	X	X		X	X
Medication Reconciliation	X	X		X	X

OPTIMATE Trial

Principal Investigator: [name] [name]

FORTA* criteria	X	X		X	X
Laboratory Results	X	X			
Electrocardiogram review	X				
EQ5D-5L				X	X
Randomization	X				
Medication History (modified SHiM)	X				
Modified Medication Adherence Rating Scale (mMARS)	X				
Barthel Index Score	X	X			
Drug-drug interactions (Stockley's)	X	X		X	X
STOPP/START criteria (PIMs & PPOs*)	X	X		X	X
Face-to-face discussion with senior attending physician or senior resident to highlight potentially inappropriate PIMs and PPOs	X	X			
Face-to-face discussion with patient or nominated proxy (where patient does not have decision-making capacity) to explain details of recommended medication changes.		X			

OPTIMATE Trial

Principal Investigator: [name] [name]

Pre-discharge medication review, documentation of agreed medication adjustments and preparation of report for patient's GP with detailed explanation of recommended medication changes.		X			
Telephone contact with patient's GP to discuss medication changes.			X		
Telephone contact with patient or nominated proxy (where patient does not have decision-making capacity) to define current list of medications, discuss any medication issues and ascertain endpoint information.				X	X
Telephone contact with patient's pharmacist to define medication currently dispensed.			X	X (if necessary)	X (if necessary)

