Telephone contact with patient's GP for endpoint ascertainment (if not available from patient or proxy).				X (if necessary)	X (if necessary)
Unscheduled Readmission Determination				X	X
Unscheduled Emergency Department Attendance Determination				X	X

Admission to residential care facility (long-term)				X	X
All-cause mortality check via registries or if necessary, with the patient's GP.				X	X

Table 1b: Schedule of events for control patients

Timepoints	1	2	3	4	5
Study Visit	Baseline (within 72 hours of admission)	Pre-discharge (within 48 hours pre-discharge)	1 Week Follow-up (within 10 days post-discharge)	1 Month Follow-up (within 30 days post-discharge)	6 Month Follow-up (between 90 and 180 days post-discharge)
	Day 1	Day variable	Day 10 (+/-3 days post-discharge)	Day 30 (+/- 7 days post-discharge)	Between Day 90 and Day 180 post-discharge
Inclusion / Exclusion criteria	X				
Decision-Making Capacity Functional Assessment	X	X**		X**	X**
Informed consent/ proxy assent	X	X **		X**	X**
Patient Demographics	X				
Medical History	X	X		X	X
Medication Reconciliation	X	X		X	X
FORTA* criteria	X	X		X	X

OPTIMATE Trial

Principal Investigator: [name] [name]

Laboratory Results	X	X			
Electrocardiogram review	X				
EQ5D-5L				X	X
Randomization	X				
Modified Medication Adherence rating Scale (mMARS)	X				
Barthel Index	X	X			
Telephone contact with patient or next-of-kin to define current list of medications, discuss any medication issues and ascertain endpoint information.				X	X
Telephone contact with patient's pharmacist to define medication dispensed.			X	X (if necessary)	X (if necessary)
Telephone contact with patient's GP for endpoint ascertainment (if not available from patient or proxy).				X (if necessary)	X (if necessary)
Unscheduled Readmission Determination				X	X
Unscheduled Emergency Department Attendance Determination				X	X

Admission to residential care facility (long-term)				X	X
All-cause Mortality check via registries or if necessary, with the patient's GP.				X	X

* PIMs – Potentially Inappropriate Medications; PPOs – Potentially inappropriate Prescribing Omissions; FORTA Fit fOR The Aged

** If necessary i.e. applies to participants who initially lacked decision-making capacity at the time of their enrolment.

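### Control patients are scheduled for 1- and 6-month calls that include discussion of medication issues, in the same task wording as the active arms, which could dilute the 90-180 day contrast

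*Combined protocol and SAP*

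**What the plan says.** Section 4.0 (Study Procedures and Schedule of Events) sets out post-discharge contacts in Table 1a for the active arms and Table 1b for controls. The patient-call row in Table 1b reads "Telephone contact with patient or next-of-kin to define current list of medications, discuss any medication issues and ascertain endpoint information". It is marked without qualification at 1 month and at 6 months. Table 1a has the same row at the same times, "to define current list of medications, discuss any medication issues and ascertain endpoint information"; only the person contacted is described differently (nominated proxy rather than next-of-kin).

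Three other places bear on what controls should receive:

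- Section 4.3 defines the control arm as "standard pharmaceutical care as it contemporaneously exists in that hospital". The synopsis adds only the modified MARS questionnaire as a sham.
- Hypothesis 1 in section 2.3 describes the definitive intervention (DI) as "supplemented by structured follow-up with patients' GPs and community pharmacists as well with patients themselves".
- The synopsis lists as DI component (vii) "follow-up contact with patients' GPs and community pharmacists at 1 week and 1 and 6 months post-discharge".

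No text limits the control call to data collection or says what the caller does when a control reports a medication problem. Section 4.3 discusses contamination of controls only through physicians who treat patients in more than one arm.

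**The concern.** By the plan's own definitions, a scheduled trial call in which medication issues are discussed with the patient belongs to the intervention and not to standard care. Giving it to controls narrows the difference that the trial sets out to measure. The introduction (section 2.1) argues that an intervention of this kind needs to continue after discharge to succeed, so the post-discharge contrast is not a side matter.

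Timing decides which endpoint is exposed. The 1-month call falls at day 30 plus or minus 7, before the 90-180 day window used for readmission, ED attendance and the composite. A problem identified and acted on at that call could prevent a control event in the window. The bias would be toward no effect.

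**Working it through.** **Step 1. Compare the post-discharge rows of the two tables.**

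| Item | Table 1a (active) | Table 1b (control) |
|---|---|---|
| Patient or proxy call | firm at 1 and 6 months | firm at 1 and 6 months |
| Pharmacist call on dispensed drugs | firm at 1 week; if necessary at 1 and 6 months | same |
| GP call on medication changes | firm at 1 week | none |
| GP call for endpoints | if necessary at 1 and 6 months | same |
| STOPP/START screen | 1 and 6 months | none |
| Stockley's interaction screen | 1 and 6 months | none |

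Firm telephone contacts per patient: active 1 + 1 + 2 = 4 (GP, pharmacist, patient); control 1 + 2 = 3 (pharmacist, patient). The difference is 4 - 3 = 1, the 1-week GP call. Component (vii) implies 2 parties x 3 times = 6 GP and pharmacist contacts. Table 1a makes 2 of them firm, and only 1 of those is absent from Table 1b.

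The two screens at 1 and 6 months are also confined to the active arms. Table 1a has no row for passing their results to the patient, GP or pharmacist at those times. Hypothesis 1 places the DI's screening as "applied following admission and pre-discharge from hospital", so the later screens may be measurement only.

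**Step 2. Which endpoints can be affected.**

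- 30-day endpoint: the call comes at day 23 at the earliest (30 - 7), so at most the last 7 days of the window follow it.
- 90-180 day endpoint: the 1-month call precedes the whole window.
- The 6-month contact takes place between day 90 and day 180, inside or at the end of the window, and adds little.

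**Step 3. How many controls.** 463 are randomized per arm; 463 x 0.7 = 324 remain after 30% attrition.

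**Step 4. The plan's sample size, and an illustration.** Section 4.3 plans "for detection of an 8% absolute reduction in readmissions", from 20% to 12%, with two-sided 5% significance, 80% power and 324 per arm. With unpooled variance, n = (1.960 + 0.842)² x (0.20 x 0.80 + 0.12 x 0.88) / 0.08² = 325.7 per arm. The pooled formula gives 329 and the arcsine formula 324.9, so the stated figure reproduces.

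Power with a pooled null variance is Φ[(d - 1.96 x √(2p̄(1 - p̄)/n)) / √((p1(1 - p1) + p2(1 - p2))/n)], with n = 324, d = p1 - p2 and p2 = 0.12. The fall in control risk is an assumption:

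| Assumed fall in control risk | Control risk p1 | Power |
|---|---|---|
| 0 points | 20% | 79% |
| 1 point | 19% | 69% |
| 2 points | 18% | 57% |

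This shows only that a design starting near 80% power has little room for dilution. It does not estimate what the calls do. The 20% is a 180-day medication-related readmission risk, which includes early events that the call cannot prevent, whereas the exposed endpoint covers unscheduled events at 90-180 days.

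**The case against.** The strongest reply is that the same words need not mean the same treatment. Active patients have had the structured history, the screening, a physician discussion, an explanation of changes and a report to the GP. Controls have had none of these, so a control call has no DI recommendations to pass on. The clause sits between listing drugs and collecting endpoints, and can be read as eliciting information. The itemised DI in the synopsis names no patient telephone call. A Manual of Operations exists and may hold a call script, though it is not among the documents. Matched calls also help to keep participants blinded. All of this stands as a reason to expect any dilution to be modest. It does not remove the mismatch between Table 1b and the definition of control.

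A reader might also infer four stronger points that the documents do not support:

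- **That the 1-week GP call is all that separates the arms after discharge.** It is the only telephone contact unique to the active arms, but the STOPP/START and Stockley's screens at 1 and 6 months are also active-only.
- **That a null result could not be told apart from an enriched control arm.** FORTA criteria and medication reconciliation are recorded in all arms at baseline, before discharge, and at 1 and 6 months, so a shift in control prescribing after the 1-month call could be seen, at least in part.
- **That power falls to 69% or 57%.** Those figures follow only from assumed dilutions. Two points would be a quarter of the full intervention's planned 8-point effect, credited to one call.
- **That assessor blinding is broken.** Section 4.3 says "the trial statistician and outcome assessors will remain blinded until the results are finalized", and the call does gather endpoint information. But readmission and ED determination are separate rows, and no text says that the caller is the outcome assessor.

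**Conclusion.** The point holds as a mismatch in the schedule with a plausible but unquantified consequence. Controls are given firm 1- and 6-month calls that include a task the plan elsewhere treats as part of the intervention. The 1-month call, due to as many as 463 controls, precedes the 90-180 day window. Any effect would pull that contrast toward no difference and would leave the 30-day endpoint largely alone.

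This rests on two assumptions: that the calls are made as Table 1b words them, and that discussion sometimes leads to action. If an unpublished script already restricts the control call to data collection, the correction is only to the table's wording. The change is worth making because it costs almost nothing; the documents do not show that the trial's result is compromised.

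**What to change.** 1. In Table 1b, delete the medication-discussion task from the patient call. Control calls then collect the medication list, EQ-5D-5L and endpoints only. A control who reports a medication problem is told to contact the GP, and the caller logs it.
2. In Table 1a, have the caller collect endpoint information first, with the same script as for controls, and discuss medication only afterwards. This limits differential ascertainment without an extra call or caller.
3. If calls have already been made, report beside the 90-180 day result any recorded control calls in which advice was given, and the control-arm change in FORTA categories from 1 to 6 months. The documents do not say that call records capture advice, so the count may be incomplete.

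Cost: item 1 is a text change that shortens up to 463 x 2 = 926 control calls (324 x 2 = 648 after attrition), plus a brief log entry when a problem is reported. Item 2 needs a common script. The small downside is that call content will differ slightly between arms; the number and timing of patient calls stay matched, so participant blinding should be little affected.

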6.0 Outcome measures

6.1 Primary Outcome

- (i) unscheduled readmission within 30 days post-discharge,
- (ii) unscheduled readmission between 90 and 180 days post-discharge, and
- (iii) ED attendance within 30 and between 90 and 180 days post-discharge.

A primary composite endpoint of unscheduled readmission or ED attendance within 30 and between 90 and 180 days post-discharge will also be ascertained.

Treatment effects for each of the two intervention arms versus the control arm will be estimated for each outcome. Equivalence tests comparing the two active arms (for each outcome) will be done to compare DI delivery by physician with DI delivery by pharmacist.

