2.0 Background and Significance of the question

2.1 Introduction

Research consistently shows that 5-6% of all acute hospitalizations result from adverse drug reactions (ADRs; Kongkaew et al.). This proportion approximately doubles in older people with multimorbidity and related polypharmacy (i.e. ≥ 5 daily prescription medications; Oscanoa et al.). Polypharmacy which results from multimorbidity predisposes to drug-related problems (DRPs), potentially inappropriate medications (PIMs), potential prescribing omissions (PPOs), medication non-adherence, medication errors and accidental overdose, all of which heighten risk of ADRs ([name]). These medication-related problems can individually or in combination lead to hospitalization, more commonly in older people (Al Hamid et al.; Thomsen et al.). A recent systematic review indicates that approximately two-thirds of hospital readmissions relating to adverse medication in older people are preventable (El Morabet et al.). Previous studies show that older people in transition from hospital to the community experience prescribing errors and problems with medication information transfer more commonly, resulting in various DRPs that are commonly detrimental to patients (Laugaland et al.). Recurrent hospitalizations (including 1-month readmissions affecting at least 21.9%-22.3% of patients (McAuliffe et al.; Ravn-Nielsen et al.) and unplanned emergency department (ED) attendances arising from potentially inappropriate medication are common in multimorbid older people, and costly (Hyttinen et al.; Leendertse et al.), but preventable. Previous studies also show that older people exposed to PIMs and PPOs in the community experience excess hospitalization and ED attendance (Xing et al.; Moriarty et al.). Hence, any definitive intervention for minimizing rehospitalization/ED attendance in multi-morbid older people should include components for minimizing PIMs and PPOs.

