More recently, a Danish RCT (OPTIMIST trial) examined the effect of a multi-faceted clinical pharmacist-delivered intervention (basic and extended) based on medication review during hospitalization compared with standard pharmaceutical care (Ravn-Nielsen et al.). The trial concluded that applying the extended clinical pharmacist intervention which included a motivational interview with patients and post-discharge follow-up with the patients' GPs and community pharmacists significantly reduced all-cause readmission within 30 days (hazard ratio [HR] of 0.62, 95% CI 0.46-0.84) and within 180 days (HR 0.75, 95% CI 0.62-0.90) and the proportion of patients experiencing the primary composite endpoint of readmission or emergency department attendance within 180 days (HR 0.77, 95% CI 0.64-0.93) compared to matched patients receiving standard pharmaceutical care. The NNT to prevent the composite primary endpoint with the extended pharmacist intervention was 12. The cost-benefit ratio of the extended pharmacist intervention is, however, unknown. The OPTIMIST trial included adult patients over 18 and randomized a total of 1498 patients. Importantly, less than 50% of randomized patients were aged over 65. In the over-65 age group, the impact of the extended pharmacist intervention was statistically significant whilst its impact in the under-65s was not significant. Furthermore, the extended intervention showed a significant effect on the primary composite endpoint in patients of all ages taking > 8 daily drugs at admission but was not significant in patients taking ≤ 8 daily drugs. That is, the extended pharmacist intervention was particularly effective in patients over 65 taking > 8 daily medications.

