2.2 Aims of the study

- (i) Primary aim: to determine if a medication optimization DI can significantly reduce all-cause re-hospitalization and unscheduled emergency department attendance at 30 days and between 90 and 180 days in multi-morbid older people exposed to polypharmacy. To achieve this, we will measure the following outcomes: Unscheduled readmission within 30 days and between 90 and 180 days post-discharge, ED attendance within 30 and between 90 and 180 days post-discharge, and a primary composite endpoint of unscheduled readmission or ED attendance within 30 and between 90 and 180 days post-discharge.
- (ii) Secondary aims:
 - (a) To determine the effects of the DI on secondary endpoints, including quality of life (EQ5D-5L), all-cause mortality and referral to nursing home for long-term care.
 - (b) To compare endpoints achieved through standard pharmaceutical care (control) with those achieved through physician-delivered DI and pharmacist-delivered DI. This is to determine if DI delivery by a trained pharmacist is more/less/equally effective compared to DI delivery by a trained physician.

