6.2 Secondary Outcome(s)

- (i) quality of life measured by EQ5D-5L instrument (incorporating pain control) at 30 days and at between 90 and 180 days post-discharge,
- (ii) all-cause mortality at 30 and between 90 and 180 days post-discharge,
- (iii) occurrence of first admission to residential care facility for long-term nursing care at 30 and between 90 and 180 days post-discharge.

The EQ-5D-5L is a self-assessed, health related, quality of life questionnaire which brings the patient (and often their carer) to the fore when attempting to measure the impact of the intervention (see Appendix 1). The scale measures quality of life on a 5-component scale including mobility, selfcare, usual activities, pain/discomfort, and anxiety/depression. It offers the patient the opportunity to express their satisfaction (or not) with the intervention received and is used to determine and quantify the benefits of the intervention.

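### The later primary endpoints share their 90-to-180-day wording with the 6-month contact, and no rule says which events count

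*Combined protocol and SAP*

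**What the plan says.** Section 6.1 gives the later readmission endpoint as "unscheduled readmission between 90 and 180 days post-discharge" and uses the same range for ED attendance and the composite. Section 2.2 repeats it in the primary aim: "significantly reduce all-cause re-hospitalization and unscheduled emergency department attendance at 30 days and between 90 and 180 days". The synopsis has "unscheduled readmission within between 90 and 180 days post-discharge", in which two time expressions have run together.

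The same range appears where it can only be a measurement time. Tables 1a and 1b head the last visit "6 Month Follow-up (between 90 and 180 days post-discharge", and endpoint information is gathered by telephone at that visit, with the GP as back-up. Section 6.2 has "quality of life measured by EQ5D-5L instrument (incorporating pain control) at 30 days and at between 90 and 180 days post-discharge".

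Other places point to a fixed 180-day horizon. Section 4.3 sizes the trial on "a known 180-day risk of medication-related readmission of approximately 20" per cent. The precedent trial described in section 2.1 used a "primary composite endpoint of readmission or emergency department attendance within 180 days". The safety outcomes section places the last FORTA assessment at day 180. For the economic analysis only, section 6.3 takes every readmission and ED attendance into account.

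Section 7.2 analyses binary outcomes by logistic regression and describes no term for length of follow-up. It defers a complete SAP to pre-registration before database lock.

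**The concern.** An endpoint needs a start of counting, an end of counting and a rule for assigning events. The later primary endpoints have a range that can be read in two ways.

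- **Event window.** Only events dated between days 90 and 180 count. Days 31 to 89 then fall outside every primary endpoint, although the economic analysis counts those events.
- **Contact window.** Events up to a call made on some day from 90 to 180 count. A readmission on day 120 is then an event if the call is on day 150 and not if it is on day 100. Observation time varies by up to 90 days between patients, and the described model treats them alike.

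The first reading does not give a cumulative 180-day risk. The second gives it only if every contact falls on day 180, which the schedule does not require. What is at stake is the meaning of the later primary results and the number of events behind them. The 30-day endpoints are the same under both readings. They need only an event-date rule, because the 1-month call may be as early as day 23 (day 30 minus 7).

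**Working it through.** **The plan's own figure.** Inputs from section 4.3: 20% versus 12%, two-sided 5%, 80% power, 30% attrition. The pooled-variance formula gives [1.960√(2·0.16·0.84) + 0.842√(0.20·0.80 + 0.12·0.88)]² / 0.08² = 328.5, so 329 per arm. The unpooled version gives 326 and the arcsine version 325. The stated 324 is reproduced closely, and 972/0.7 = 1388.6 gives 1389. The arithmetic is sound, and it fits a cumulative count from discharge to day 180.

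**Power at 324 per arm.** Power = Φ{(|p₁−p₂|√n − 1.96√(2p̄(1−p̄))) / √(p₁(1−p₁)+p₂(1−p₂))}. For 20% versus 12%: (0.08·18 − 1.016)/0.515 = 0.822, so power is 79.5%.

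**Assumptions for the other readings.** The documents give no event timing, so a curve has to be assumed: S(t) = exp[ln(1−R)·(t/180)^k], with R = 0.20 for control and 0.12 for intervention. This implies a constant hazard ratio of ln 0.88 / ln 0.80 = 0.573. Shape k = 1 is a constant hazard; k = 0.5 is front-loaded.

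- Contact window: average of 1−S(t) over the contact days.
- First events in the window only: S(90)−S(180).
- Any event in the window: 1−S(180)/S(90), assuming that events after day 90 occur independently of earlier ones.

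| What is counted | Risks, k = 1 | Power | Risks, k = 0.5 | Power |
|---|---|---|---|---|
| Discharge to day 180 | 20.0% v 12.0% | 79.5% | 20.0% v 12.0% | 79.5% |
| To contact, even over days 150–180 | 18.5% v 11.1% | 76% | 19.2% v 11.5% | 78% |
| To contact, even over days 90–180 | 15.4% v 9.1% | 68% | 17.5% v 10.4% | 74% |
| Any event in days 90–180 | 10.6% v 6.2% | 52% | 6.3% v 3.7% | 34% |
| First events in days 90–180 | 9.4% v 5.8% | 41% | 5.4% v 3.4% | 25% |

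**Share of control first events on days 31 to 89.** (S(30)−S(90))/0.20 = (0.9635−0.8944)/0.20 = 34.5% for k = 1, and (0.9129−0.8540)/0.20 = 29.4% for k = 0.5.

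**Limit of the illustration.** These curves put control risk at day 30 at 3.7% or 8.7%, whereas section 2.1 cites "1-month readmissions affecting at least 21.9%-22.3% of patients". The 20% is for medication-related readmission, and the listed endpoints are broader. If the base risk were 45% by day 180 (an assumption), a full day-180 count would have 98.9% power at the same hazard ratio but 54% for the same 8-point reduction. The table compares counting rules; it does not forecast power.

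**The case against.** **The range is obviously a visit window.** The EQ5D-5L wording and the schedule favour this. It narrows the problem but does not remove it, because observation could still end anywhere in a 90-day span. The documents also do not state that counting stops at the call: the schedule lists readmission and ED determination as rows separate from the telephone contacts, with GP back-up. Dependence on the call date is therefore a plausible inference, not a stated rule.

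**Contacts will cluster near day 180.** The 6-month label and the day-180 FORTA assessment suggest late calls. With contacts over days 150 to 180 the illustrated loss is only about 2 to 3 points. This stands, but nothing in the schedule requires late calls.

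**The SAP will settle it.** A counting rule can properly be set there. A SAP finalised late cannot supply events that followed an early call unless someone ascertained them, so ascertainment has to be fixed during follow-up.

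**A stated 90-to-180-day event window would be just as clear.** True, but it would give up the 180-day horizon used for sizing and leave days 31 to 89 out of every primary endpoint.

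A reader might infer three stronger things. One is that the trial is underpowered: the documents give no event timing, and their base risk is for a different event. Another is that the arms are biased: no passage suggests that call timing differs by arm, and section 4.3 says outcome assessors are blinded. The third is that one of the listed endpoints was sized and then lost: the sizing risk is medication-related, so it matches no listed endpoint in type, which is a separate mismatch.

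**Conclusion.** The concern holds as a missing definition. The later primary endpoints can be read in two ways, and neither reliably yields the cumulative 180-day risk used for sizing and in the cited precedent. That conclusion comes from the text and needs no assumption.

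The size is illustrative only. Under 20% versus 12% by day 180, proportional hazards and 324 per arm, power moves from 79.5% to 68–78% under the contact readings shown and to 25–52% under the literal event window. There is no loss if every contact falls on day 180. The actual effect on power is unknown and no between-arm bias is shown. It should be fixed: the later primary endpoints are affected, and early action matters because unascertained events may not be recoverable.

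**What to change.** - **Definition.** Define the later endpoints as any unscheduled readmission, any ED attendance, and either of them, from discharge through day 180 by event date. Define the early ones the same way through day 30. Use one wording in the synopsis and in sections 2.2 and 6.1.
- **Ascertainment.** Establish status to day 180 by the same rule in all three arms, through the patient, proxy and GP contacts already scheduled, with a later check for anyone contacted before day 180. Record event dates and the date of last ascertainment.
- **Analysis.** Keep the logistic regression of section 7.2, adjusted for centre and service type, as the single primary analysis. State in the SAP, before database lock, how deaths and incomplete ascertainment are handled. Add time to first event, censored at last ascertainment, as a sensitivity analysis, not as a replacement chosen after seeing the data.

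**Cost.** No extra patients; wording changes, plus a later check for some patients. Consent coverage for that check should be confirmed: the inclusion criteria cover contact up to 180 days after discharge. If the synopsis end date of 15/07/2024 reflects day-90 contacts, the last endpoint date could move by up to 90 days, to 13/10/2024. That is 17 days past 24 months from the 26/09/2022 start (the section 3.1 objective) and 48 days before the 30/11/2024 analysis date. If the end date already reflects day 180, nothing moves.
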